3.3.5.2 Sample Size

Each group will consist of 15 study subjects for the purpose of convenience and the total sample size will be 75.

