3.3.6 Treatment Plan

For this phase of the study, 4 best treatment combinations of pre-biotics and iron fortificants will be chosen based on the results of animal trials while one group will be taken as control (Table 1).

Table 1: Treatment Plan for Anemic Women

GROUP	DIET PLAN
D ₀	Control Group (Placebo)
D ₁	Best Treatment Combination 1
D ₂	Best Treatment Combination 2
D ₃	Best Treatment Combination 3
D ₄	Best Treatment Combination 4

Study participants will be randomly chosen to receive either the best treatment combination 1, 2, 3, 4 or the placebo for 12 weeks on daily basis.

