3.3.7 Efficacy Trials

Up to three months, blood samples will be collected from overnight fasted women on monthly basis.

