3.3.7.6 Statistical Analysis

In order to determine the level of significance, the statistical analysis of the obtained data will be done for the purpose of which, SPSS version 23.0 will be used. CRD will be used during the experiment and differences will be considered significant at P - value < 0.05 (Steel and Torrie 1980).

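### The only named analysis is a CRD, and nothing in the plan stops the repeated monthly samples from each woman being pooled under its single error term; if they are, the 0.05 level fails

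*Combined protocol and SAP*

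**What the plan says.** The whole analysis plan is section 3.3.7.6. It names SPSS 23.0, refers without restriction to the data obtained, and adds "CRD will be used during the experiment and differences will be considered significant at P - value < 0.05". It gives no model, factor list, error term, primary month or per-woman summary.

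Three other sections fix the structure of the data:

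- Section 3.3.7 (Efficacy Trials): "Up to three months, blood samples will be collected from overnight fasted women on monthly basis". That is three values per woman, or four if a pre-treatment sample is also taken, which the text does not settle.
- Section 3.3.6 (Treatment Plan): "Study participants will be randomly chosen to receive either the best treatment combination 1, 2, 3, 4 or the placebo for 12 weeks". Allocation is by woman, to five groups.
- Section 3.3.5.2 (Sample Size): "Each group will consist of 15 study subjects for the purpose of convenience and the total sample size will be 75".

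No section names a repeated-measures or mixed model.

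**The concern.** The one method named does not match the data that the protocol will generate. A CRD analysis treats each value as a separate experimental unit. Here the unit is the woman, and successive values from one woman will usually be correlated. If all monthly values go into one CRD analysis, repeat samples count as extra women.

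For comparisons between arms, the error is then understated and chance differences can pass as efficacy for any of the four combinations. For comparisons over time, the opposite happens: stable differences between women stay in the error term, so real changes and real divergence between arms can be missed. The same sentence of the plan would also cover a valid analysis, which leaves the choice of error structure open until the data have been seen.

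**Working it through.** **Inputs from the documents.** Five arms of 15 women: 5 × 15 = 75, which reproduces the stated total. Significance level 0.05 (sidedness not stated; pairwise tests are taken as two-sided below). Samples per woman m = 3, or 4 with a pre-treatment sample. There is no power figure to reproduce, since group size was set "for the purpose of convenience".

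**Assumption.** The correlation rho between two monthly values from the same woman is not in the documents. It is taken as equal for all pairs of months and shown at 0.1, 0.5 and 0.8, with normal data and no missing values.

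**Degrees of freedom.** Pooling gives 75 × 3 = 225 values (75 × 4 = 300). The error df are 225 − 5 = 220 (300 − 5 = 295) for an arm-only CRD, or 225 − 15 = 210 (300 − 20 = 280) for an arm-by-month CRD. Only 75 − 5 = 70 df exist between women.

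**Arm comparisons.** True SE divided by reported SE is √(1 + (m − 1)rho). At m = 3 and rho = 0.5 this is √(1 + 2 × 0.5) = √2 = 1.41. A pairwise test at nominal 5% then has error 2 × (1 − Φ(1.96/1.41)) = 16.6%. The five-arm F test was simulated under the null, 8,000 runs per setting.

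| m | rho | SE too small by | Pairwise error | F test, arm-only CRD | F test, arm-by-month CRD |
|---|---|---|---|---|---|
| 3 | 0.1 | 1.10 | 7.4% | 9.5% | 9.3% |
| 3 | 0.5 | 1.41 | 16.6% | 32% | 31% |
| 3 | 0.8 | 1.61 | 22.4% | 46% | 44% |
| 4 | 0.1 | 1.14 | 8.6% | 12% | 11% |
| 4 | 0.5 | 1.58 | 21.5% | 45% | 44% |
| 4 | 0.8 | 1.84 | 28.8% | 61% | 59% |

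Independent simulations agree to within a percentage point or two. At rho = 0.8 and m = 3, the 45 values in an arm carry the information of 45/2.6 = 17 independent ones.

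**Time comparisons, only if month is a factor under the same error term.** Reported SE divided by true SE is 1/√(1 − rho): 1.05 at rho 0.1, 1.41 at 0.5 and 2.24 at 0.8. At rho 0.5 the nominal 5% month test rejects a true null about 0.2–0.4% of the time, and the arm-by-month test 0.03% or less.

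**Valid alternatives in the same simulation.** With separate between-woman (70 df) and within-woman (140 or 210 df) error terms, the arm, month and arm-by-month tests reject 4.3–5.4% of the time at every rho tried. A one-way CRD on one month, with one value per woman, rejects 4.7–5.2%.

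**The case against.** The strongest reply is that the plan never says the months will be pooled. The words "CRD will be used during the experiment" can be read as describing the allocation layout, and a CRD analysis at one month, or on one value per woman, fits the text equally well and is valid. This stands. A reader might infer that the plan commits to treating repeat samples as separate women; the documents do not support that. They support only that pooling is not ruled out.

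Three further limits also stand.

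- **Size.** A reader might infer that the distortion is bound to be large. It depends on rho, which is not given: at 0.1 the standard errors are off by only 5–14%, and at 0.5 or above by 41% or more. Even at 0.1, though, the F test runs at about twice its nominal level.
- **Trend.** An arm-only one-way CRD produces no trend standard error, so the wide trend error arises only if month is added as a factor. The plan names neither model.
- **Power.** A reader might infer that a plain CRD sacrifices power for the month-3 comparison. It does not. Suppose all four combinations are 1 SD above placebo at month 3. The noncentrality is then 15 × (0.8² + 4 × 0.2²) = 12, and a one-way F(4, 70) test has 77% power. With complete data and no baseline covariate, the mixed model gives the same month-3 estimates.

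What does not stand is the conclusion that no change is needed. One sentence that covers both a 5% test and a test with a false-positive rate of roughly 10–60% does not secure the stated level.

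**Conclusion.** The concern holds in conditional form. The plan names a single-error design for data that are repeated within women, and does not say how the repeats enter the analysis. If the monthly values are pooled, the five-arm test at nominal 5% has a false-positive rate of about 10% to 46% with three samples per woman, and about 11% to 61% with four, over an assumed correlation of 0.1 to 0.8. The figures rest on equal correlation between months, normal data and complete sampling. The direction of both errors needs only positive correlation within women. The specification must be fixed before analysis because the trial's only error-rate statement depends on it. The point concerns independence of repeat samples alone, not multiplicity, baseline adjustment or missing data.

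**What to change.** In section 3.3.7.6, keep CRD as the description of the allocation only, and replace the analysis wording with text to this effect:

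- *Monthly values will be analysed with a linear mixed model (SPSS MIXED) with arm, month and arm-by-month as fixed effects, the woman as the repeated subject, and an unstructured covariance. Arm differences at month 3 will be estimated from this model and tested at the 0.05 level.*
- *Any one-way CRD analysis will use one value per woman (month 3). Monthly values will never be pooled as independent observations.*

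The gain is a protected error rate for arm comparisons and correct error terms for month and arm-by-month. It should not be presented as extra power for the month-3 contrast.

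The cost is a few sentences of analysis wording. The software and data stay the same, with no extra women or samples and no change to clinical procedures.

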3.3.7.7 Ethical Considerations

The approval of the study will be taken from the Institutional Review Committee for Biomedical Research of the University of Veterinary & Animal Sciences, Lahore. Moreover, informed written consent will be obtained from all the study subjects. In addition to this, privacy and confidentiality of the data of all the study subjects will be ensured.
